#### As-Treated Population (AT):

This population consists of all treated subjects regardless of whether they become pregnant or undergo weight change during the study.

**Safety Population (SA):**

This population will consist of all treated subjects with safety evaluation after the treatment. This population should be identical to the AT population. The safety data analyses will be performed based on the Safety Population.

**Sample Size Requirement**

[figure not shown]
The sample size of this study (45) was selected as it is thought to be appropriate to provide preliminary information regarding safety and efficacy of using the CoolMini vacuum applicator for contouring along the jawline.

**3.16.3. Endpoint Analysis**

**Primary Safety Endpoint:**

The primary safety endpoint is measurement of unanticipated adverse device effects. All adverse events reported during and following the treatment will be included in the safety analysis. The frequency and proportion of subjects reporting each type of adverse event will be tabulated by relationship with the treatment and severity of the event.

**Primary Efficacy Endpoint: Photographic Review**

**Secondary Endpoint: Reduction in Fat Layer Thickness as Measured by Ultrasound**

11. **What is the primary purpose of the following statement?**

12. **What is the primary purpose of the following statement?**

### **Secondary Endpoint: Subject Satisfaction**

The number and percentage of subjects will be summarized for each possible point grade of the satisfaction questionnaire at 12-weeks. The percentage of subjects who responded as satisfied or very satisfied will be provided, [REDACTED]

subjects who responded as dissatisfied or very dissatisfied will also be calculated.

### 3.17. *Protocol Adherence*

The study investigators are responsible for performing the study in compliance with the protocol. Non-adherence to the protocol is to be classified as a protocol violation, protocol deviation, or protocol exemption, as defined below.

## Protocol Violation

Non-adherence to the protocol that may result in significant additional risk to the subject (e.g., enrollment of a subject who does not meet the study criteria). Or, non-adherence to Good Clinical Practices (GCP) that may impact patient safety (e.g., failure to obtain proper consent prior to performing study procedures). Violations should be reported to the study Sponsor and the IRB within 5 working days if they occur.

## Protocol Deviation

Non-adherence to study procedures which does not result in additional risk to the subject (e.g., subject missed visit). Protocol deviations are not required to be reported to the IRB; however, they must be recorded on the study case report forms and may be reported and reviewed in conjunction with the progress report as part of the annual review process.

### 3.18. Adverse Events

Adverse events (AE) will be assessed continuously throughout the study. An adverse event is defined as any untoward medical occurrence in a subject, regardless of whether the event is related to the device.

ZELTIQ P/N:

Protocol Number: ZA17-004

This document and the contents hereof are considered proprietary and confidential information of ZELTIQ Aesthetics, Inc. Disclosure to unauthorized individuals or dissemination, publication or copying is prohibited without prior written consent of ZELTIQ.

### **Adverse Device Effect (ADE)**

Any sign, symptom, or disease in a study subject that occurs during the course of a clinical trial that is determined by the investigator to have a causal relationship or possible causal relationship with the device under investigation.

### **Serious Adverse Event (SAE)**

Any untoward medical occurrence in a subject, regardless of whether the event is related to the device that:

- a. results in death;
- b. results in a life threatening illness or injury;
- c. results in a permanent impairment of a body structure or body function;
- d. requires in-patient hospitalization or prolongation of existing hospitalization
- e. results in medical or surgical intervention to prevent impairment to body structure or function;
- f. results in fetal distress, fetal death, or a congenital abnormality/birth defect.

### **Unanticipated Adverse Device Effect (UADE)**

Any serious adverse effect on health and safety or any life-threatening problem or death caused by, or associated with a device, if that effect, problem, or death was not previously identified in nature, severity, or degree of incidence in the investigational plan or application, or any other unanticipated serious problem associated with a device that relates to the rights, safety, or welfare of subjects.

The Investigator shall be responsible for determination of the causal relationship of all adverse events to the device and/or procedure. The Principal Investigator is responsible for monitoring the safety of the subjects enrolled.

The Sponsor is responsible for the ongoing safety evaluation of the product(s). The Sponsor shall be responsible for adjudication of all reported adverse events to determine whether the event is reportable under federal regulations (i.e., 21 CFR812.150[b][1]). The Sponsor will promptly notify all participating investigators and regulatory authorities, as appropriate, of findings that could affect adversely the safety of subjects, impact the conduct of the trial or alter the IRB's approval opinion to continue the trial.

### **3.19. Reportable Incidents**

Serious adverse events (SAEs) and unanticipated adverse device effects (UADEs) must be reported within 24 hours of knowledge of the event to the Sponsor:

ZELTIQ P/N: [REDACTED]

Protocol Number: ZA17-004

This document and the contents hereof are considered proprietary and confidential information of ZELTIQ Aesthetics, Inc. Disclosure to unauthorized individuals or dissemination, publication or copying is prohibited without prior written consent of ZELTIQ.

A full reporting of the event shall be provided within 10 working days of the event. The Sponsor is then responsible for notifying the IRB, as required.

## **4. Study Management and Quality Control**

### **4.1. *Study Data Collection***

Standardized Case Report Forms (CRFs) will be provided to all participating sites. Data will be reviewed by the study monitor and Sponsor data management personnel to identify inconsistent or missing data and to ensure compliance with the study protocol.

### **4.2. *Confidentiality***

All information and data concerning study subjects will be considered confidential, and handled in compliance with all applicable regulations including the requirements of the Health Insurance Portability and Accountability Act (HIPAA) of 1996.

Only authorized site staff, the study Sponsor or the Sponsor's designee and IRB will have access to these confidential files. A unique identification code will be assigned to each subject participating in this trial. All data used in the analysis, reporting and publication of this clinical trial will be maintained without identifiable reference to the subject. Any data that may be published in abstracts, scientific journals, or presented at medical meetings will reference a unique subject code and will not reveal the subject's identity.

### **4.3. *Investigator Responsibilities***

#### **4.3.1. *General Responsibilities***

Investigators are responsible for ensuring the investigation is conducted according to all signed agreements, the Investigational Plan, and applicable regulations. The investigator must protect the rights, safety, privacy and welfare of the subjects under the Investigator's care. Investigators will assume overall responsibility and accountability for study site staff and for the clinical data obtained during the study. The investigator assumes all responsibilities per applicable regulations, including but not limited to:

## IRB Approval

The investigator may not begin the study until the governing institutional review board (IRB) provides written approval of the study protocol and consent form. The investigator is also responsible for fulfilling any conditions of approval imposed by the IRB.

## Informed Consent

The investigator must ensure that informed consent is obtained from each prospective study subject and that the study is not commenced until IRB approval has been obtained.

## Device Accountability

Device accountability is not applicable for this non-significant risk study.

## Financial Disclosure

Investigators shall provide financial disclosure according to federal regulations.

## Study Coordinator

To assure proper execution of the study protocol, each investigator must identify a study coordinator for the site who will work with and under the authority of the investigator to assure that study requirements are fulfilled as appropriate.

### 4.3.2. Investigator Records

The investigator and study staff must maintain accurate, complete, and current records relating to the conduct of the investigation. Records must be retained for a period of two years following (1) the date the investigation was completed or terminated, or (2) the records are not longer required to support a regulatory submission or completion of a product development protocol, whichever is longer. Participating investigators shall maintain the following:

- All correspondence with the Sponsor, another investigator, the IRB, and a monitor
- Records of all persons authorized to conduct the study (e.g. Delegation of Duties/Signature Authorization, CV)
- Records of receipt, use or disposition of the device
- Informed Consent documentation for all enrolled subjects
- Records of each subject's case history, including study-required Case Report Forms and source documentation (e.g. physician notes, lab reports, study worksheets, clinic charts)

- All relevant observations of adverse device effects
- Records of any protocol deviations
- The condition of each subject upon entering and during the course of the investigation and any relevant medical history and results of any diagnostic tests
- Record of each subject's exposure to the device, including the date and time of use
- Investigational plan with all amendments
- Current IRB approved informed consent and all previously approved versions
- Signed Investigator agreement
- Investigators will be responsible for the accurate and timely completion of CRFs during the trial.

These records must be available and suitable for inspection at any time by Sponsor representatives (monitor), or the reviewing IRB. The Investigator will supply access to study-related medical records, original laboratory data, and other records and data as they relate to the trial. The investigator will ensure that both he/she and his/her study staff have adequate time and resources to devote to the study, including study enrollment, subject evaluations, study documentation and site monitoring.

#### **4.3.3. Investigator Reports**

The investigator is responsible for preparation and submission of the following reports:

- Report of any unanticipated adverse device effects shall be submitted to the Sponsor within 24 hours and no later than 10 working days after the Investigator first learns of the effect.
- Withdrawal of IRB approval of the investigator's part in the investigation shall be reported to the Sponsor within 5 working days.
- Progress reports on the investigation to the sponsor, the monitor, and the reviewing IRB annually. Alternatively, the Sponsor may prepare the report.
- Deviations from or violations of the investigational plan shall be reported to the Sponsor, and the IRB as required.
- Failure to obtain informed consent prior to use of a device in a subject shall be reported to the Sponsor and IRB within 5 working days after the use occurs.

ZELTIQ P/N: [REDACTED]

Protocol Number: ZA17-004

This document and the contents hereof are considered proprietary and confidential information of ZELTIQ Aesthetics, Inc. Disclosure to unauthorized individuals or dissemination, publication or copying is prohibited without prior written consent of ZELTIQ.

A final report shall be submitted to the Sponsor and IRB within 3 months after termination or completion of the investigation, or the investigator's part of the investigation.

## **4.4. Sponsor Responsibilities**

### **4.4.1. General Responsibilities**

As the Sponsor, ZELTIQ assumes overall responsibility for the conduct of the study including assurance that the study satisfies FDA regulatory requirements. ZELTIQ assumes all responsibilities per applicable regulations, and shall:

#### **IRB approval**

Ensure IRB approval for the investigation. Ensure IRB approval for a supplemental application before beginning that portion of the investigation.

#### **Investigators**

Select investigators qualified by training and experience, and providing them with the information they need to conduct the investigation properly. Obtain a signed Investigator Agreement from each participating investigator. Study sites will be evaluated to ensure that they have an adequate subject base and can provide sufficient staff and documentation support to conduct the study properly.

#### **Monitoring**

Select monitors qualified by training and experience to monitoring the study ), and ensure proper monitoring of the investigation.

#### **Investigational devices**

Not applicable. This is a non-significant risk study

#### **Data Management and Analysis**

Ensure data collection, verification, analysis, records storage, etc. Sponsor will assist with presentation(s) and/or publication(s).

### **4.4.2. Training**

#### **Study Training**

To ensure uniform data collection and protocol compliance, Sponsor personnel will provide an educational session to study site personnel as needed, which will cover the protocol, techniques for the identification of eligible subjects, data collection and form completion, and the device

ZELTIQ P/N: [REDACTED]

Protocol Number: ZA17-004

This document and the contents hereof are considered proprietary and confidential information of ZELTIQ Aesthetics, Inc. Disclosure to unauthorized individuals or dissemination, publication or copying is prohibited without prior written consent of ZELTIQ.

directions for use. The investigator and study staff will be trained on the study device and protocol, applicable regulations and requirements, and expectations of the study, enrollment expectations, subject selection, informed consent, required clinical data and record keeping, etc.

### **Device Use and Procedure**

Representatives of the Sponsor will train study site staff in use of the study device. Sponsor representatives may be present at study procedures.

#### **4.4.3. Monitoring**

The Sponsor will ensure that qualified clinical monitors are available to monitor and oversee the conduct of the trial and that monitoring is performed in accordance with the Sponsor's approved procedures or third-party procedures approved by the Sponsor.

The clinical monitors will evaluate compliance with the protocol, any specific recommendations made by the site's IRB and the signed Investigator Agreement.

### **Site Qualification Visit**

A pre-study meeting will occur with the study site to evaluate the site's qualification to conduct the study.

### **Monitoring Visits**

On-site monitoring visits will assess the progress of the clinical study and identify any concerns that result from device performance or review of the investigator's study records, study management documents, and informed consent documents.

Monitoring will ensure continued protocol compliance, accurate data reporting, and adequate accounting of shipments of study devices. Monitoring visits will occur at regular intervals.

During monitoring visits, the monitor will compare subject records and other supporting documents with reports at the site to determine that:

### **Study Site Closeout**

At the close of the study at a clinical site, the monitor will conduct site close out per Sponsor's standard procedure.

#### **4.4.4. Final Report**

A final report will be prepared at the conclusion of the trial. A copy of the final report will be provided to each investigator and to the respective IRBs.

#### **4.4.5. Trial Registration**

Prior to study initiation, the trial will be registered on a publicly accessible study database such as clinicaltrials.gov when applicable.

### **5. Data Ownership**

ZELTIQ, the study Sponsor, retains ownership of all data generated in this study, and controls the use of the data for purposes of regulatory submissions to the US and/or other governments. Investigator(s) and institution(s) (which shall include their employees, agents, and representatives) may not issue or disseminate any press release or statement, nor initiate any communication of information regarding this study (written or oral) to the communications media or third parties without the prior written consent of the Sponsor.

### **6. Publication Policy**

Participating investigators and/or Institutions may publish information or data collected or produced as a result of participation in appropriate scientific conference or journals or other professional publications subject to written permission from the Sponsor, provided that drafts of the material are provided to the Sponsor for purposes of review and comment at least sixty (60) days prior to the first submission for publication or public release. Investigators may not publish information regarding site-specific data until a multicenter study report has been published.

### **7. Risk/Benefit Analysis**

The Sponsor has undertaken a comprehensive risk-benefit analysis.

#### **7.1. Benefits**

Fat reduction in the treatment area is anticipated to provide an aesthetic benefit and the use of this non-invasive system may eliminate the need for an invasive procedure that requires anesthesia or recovery time. Considering the number of surgical procedures performed for the removal of fat each year (1.5 million procedures worldwide, according to the 2016 International Society of Aesthetic Plastic Surgeons Biennial Global Survey), the use of such a non-invasive procedure has the potential to significantly reduce the incidence of complications and post-surgical limitations associated with those procedures.

#### **7.2. Risks**

Although this study presents minimal risks to the subject, there is the potential for some risk when any medical procedure is performed.

## Anticipated Device Effects

These are known effects of the ZELTIQ Procedure, previously recorded in prior studies as transient and/or temporary effects related to the cold application and/or vacuum pressure inherent in the treatment. Anticipated effects of the device which will not be considered adverse events include:

- inflammation of the subcutaneous fat layer, which is a desired effect of the procedure;
- sensations of coldness, stinging, burning, pinching, or pressure associated with placement of the applicator and the initiation of the cold treatment;
- known skin effects (e.g., blanching; erythema, bruising, purpura, petechiae, swelling, discomfort, tenderness, or soreness at the treatment site, all mild to moderate in nature) which are temporary effects that resolve spontaneously shortly after the procedure;
- localized sensory changes (e.g., numbness, tingling) at the treatment area resolving within 12 weeks of the procedure;

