### 3.14.1. Safety Assessments

The primary safety endpoint is the rate of device- or procedure-related adverse events 12 weeks post 2nd treatment. Safety will be monitored by documentation of adverse events and clinical assessment of the treatment site.

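### Section 7.2 takes listed mild-to-moderate device effects out of the adverse events, 3.18 does not mention this, and the safety paragraph of 3.16.3 names no table in which these collected effects would appear

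*Combined protocol and SAP*

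**What the plan says.** **Exclusion.** Under Anticipated Device Effects, section 7.2 says: "Anticipated effects of the device which will not be considered adverse events include". The list covers fat-layer inflammation, sensations when the applicator is placed, and mild-to-moderate skin effects such as erythema, bruising, swelling and soreness, "which are temporary effects that resolve spontaneously shortly after the procedure". It also covers "localized sensory changes (e.g., numbness, tingling) at the treatment area resolving within 12 weeks of the procedure".

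**Definitions.** Section 3.18 says: "An adverse event is defined as any untoward medical occurrence in a subject, regardless of whether the event is related to the device". It defines an adverse device effect as a sign, symptom or disease "determined by the investigator to have a causal relationship or possible causal relationship with the device under investigation". Neither definition carries an exception or points to 7.2.

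**Endpoint.** Section 3.14.1 says: "The primary safety endpoint is the rate of device- or procedure-related adverse events". Section 3.16.3 instead names unanticipated adverse device effects as the primary safety endpoint. Section 3.18 describes these as "Any serious adverse effect on health and safety or any life-threatening problem or death caused by, or associated with a device", with the further condition that the effect was not previously identified.

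**Collection.** Section 3.14.1 says: "Safety will be monitored by documentation of adverse events and clinical assessment of the treatment site". Sections 3.13.1 and 3.13.2 ask about the condition of the treated area and pain at weeks 1 and 3, listed separately from adverse events. Sections 3.13.3 and 3.13.4 require skin findings and altered sensation to be assessed at weeks 6 and 12.

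**Output.** The safety paragraph of 3.16.3 promises one tabulation: subjects with each type of adverse event, by relationship and severity. Section 3.16.1 gives a general rule for summarising data and does not name treatment-site or sensory findings.

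**The concern.** This is a single-arm study of a cosmetic procedure on the face, and safety is half of its stated purpose. Bruising, swelling, soreness and numbness are among the effects that the protocol itself expects from the device. Whether they count as adverse events is decided by a sentence in the risk section, while the section that defines adverse events is silent about it.

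Two things follow. First, if 3.14.1 governs, the value of the primary safety endpoint depends on whether the 7.2 exclusion is applied. Second, whichever primary endpoint governs, once 7.2 is applied a reader of the adverse event table cannot tell how many subjects had mild-to-moderate bruising, swelling or numbness, although the sites will have recorded it.

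**Working it through.** The plan states no figure on this point, so there is none to reproduce. The check sets the texts side by side and adds one line of arithmetic.

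**1. Do the definitions agree?** A subject with moderate numbness that resolves before week 12 and is attributed to the device has an adverse device effect by the wording of 3.18, and arguably an adverse event. By 7.2 the same subject has no adverse event. Nothing in 3.18 tells the site which rule to use.

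**2. Where would the finding be reported?**

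| Step | Text | Result for an anticipated effect |
|---|---|---|
| Collected? | 3.13.1 to 3.13.4, 3.14.1 | Yes, as safety data |
| Counted as an adverse event? | 7.2 | No |
| In the safety table of 3.16.3? | Adverse events only | No |
| In another named summary? | 3.16.1 | Permitted, not named |

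**3. Direction and size.** Let n be the number treated. Let R be the subjects with at least one device- or procedure-related event under 3.18 alone, and k those among them whose only related effects are on the 7.2 list. Read the rate as a proportion of subjects (an assumption).

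- Under 3.18 alone: R/n.
- With 7.2 applied: (R − k)/n.
- Difference: k/n, which cannot be negative.

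At the maximum n = 45 (sections 3.6 and 3.16.2), one subject is worth 1/45 = 2.2 percentage points. The documents give no incidence, so k may lie anywhere from 0 to 45.

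**4. Effect on the other endpoint.** Unanticipated adverse device effects are serious and not previously identified. The listed effects are foreseen, and the skin effects are limited to mild or moderate. If the 3.16.3 version governs, the exclusion hardly touches the primary endpoint.

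**5. Is the boundary of the exclusion stated?** Compare the two lists in 7.2:

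| Effect | Anticipated if | Listed as an adverse effect if |
|---|---|---|
| Bruising, swelling | mild to moderate, resolves *shortly* | severe, or over 1 month |
| Erythema | mild to moderate, resolves *shortly* | severe, or over 2 weeks |
| Discomfort, tenderness, soreness after the procedure | mild to moderate, resolves *shortly* | leads to medical intervention; no duration given |
| Numbness, tingling | resolves within 12 weeks | lasts over 12 weeks |

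The sensory limits meet. For bruising, swelling and erythema the second list gives durations but does not say that they define *shortly* in the first. For discomfort, tenderness and soreness there is no duration limit in either list.

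**The case against.** The strongest reply is that 7.2 is a specific, explicit rule and 3.18 a general definition in the same protocol, so the specific rule qualifies the general one. On that view the missing cross-reference is editorial. This is a reasonable reading and probably the intended one. It does not remove the reporting gap, because that gap arises precisely when 7.2 is applied.

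It can also be said that 3.16.1 allows any collected data to be summarised, and that a preliminary study of at most 45 subjects need not list every table. This stands in part. Nothing bars a summary of site findings; the point is only that none is named. Endpoint text in sections 1 and 3.15 is redacted or missing, so a provision there cannot be ruled out, although the safety paragraph of 3.16.3 appears complete.

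Three stronger readings are tempting and are not supported:

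- A reader might infer that a moderate bruise or swelling seen at the week-3 contact cannot be classified. The 1-month limits in 7.2 point naturally to treating it as anticipated. What is missing is the stated link.
- A reader might infer that numbness still present at a final visit held before week 12 is lost. Sections 3.13.1 and 3.13.2 require weekly contact until resolution for anything reported at weeks 1 or 3, and 3.13.5 allows extra visits, so most such cases are covered.
- A reader might infer that significant harms are hidden. Severe, prolonged or medically treated effects are listed in 7.2 as adverse effects.

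**Conclusion.** The point holds as a gap in reporting and a lack of reconciliation between sections; it does not show that the safety analysis is invalid. Followed as written with 7.2 applied, the only named safety table leaves out mild-to-moderate device effects that the trial collects as safety data. The related-adverse-event rate can then only be lower than, or equal to, the rate under 3.18 alone. The amount is k/45 at full enrolment, with k unknown.

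The consequence for the primary endpoint depends on 3.14.1 being the governing statement. If 3.16.3 governs, the primary endpoint is nearly unaffected and only the descriptive side-effect profile suffers. The two readable statements differ, and redacted text may settle which applies. The plan should be changed because the remedy is cheap and affects what the trial can say about safety.

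**What to change.** 1. In 3.16.3, add a Safety Population table beside the adverse event table. Give the number and percent of subjects with each anticipated effect by visit, with severity and duration where recorded, and a row for effects unresolved at last contact.
2. Report the proportion of subjects with any device- or procedure-related effect twice: without and with anticipated effects.
3. Reconcile 3.14.1 with 3.16.3 so that one primary safety endpoint is stated, and have 3.18 refer to 7.2. Reconcile *shortly* in the anticipated list with the durations and intervention criteria in the adverse effects table. Where the clinical boundary lies is for the sponsor to state.

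**Cost.** Wording and one table, with no new visit. The side-effect profile will look less favourable. Early severity data may be incomplete: 3.13.1 to 3.13.4 do not say that site or sensory findings are graded, altered sensation is named only at weeks 6 and 12, and Table 2 marks no treatment-site assessment at weeks 1 and 3. If the case report forms, which are not in the documents, have no grading field, either one is added or the table shows presence only.
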